Washing blood products prior to transfusion has been shown to reduce inflammatory markers in pediatric cardiac surgery patients²¹ and improve survival in patients with acute leukemia²² However, widespread adoption of this practice has been limited by ongoing equipoise regarding its clinical impact as well as the logistical limitations of washing RBCs in the blood bank prior to transfusion.⁸ Our preliminary data demonstrate that: **A** we can predict which patients will receive RBC transfusions, thereby facilitating the targeted enrollment of a high-risk cohort, and **B** we can effectively remove BRMs from allogeneic LR-RBC units with a practical, point-of-care, Autotransfusion device. Therefore, to demonstrate the safety, efficacy, feasibility and clinical impact of this approach, we propose the following specific aims and testable hypotheses.

AIM 1: *To determine the feasibility, safety, and efficacy of point-of-care RBC washing using the Continuous Autotransfusion System (CATS) in adult cardiac surgery patients receiving allogeneic LR-RBC transfusion.*

Aim 1a - We hypothesize that point-of-care washing of allogeneic LR-RBCs will be feasible in the time-sensitive environment of cardiac surgery with minimal or no protocol violations.

Aim 1b - We hypothesize that when compared to standard-issue allogeneic LR-RBCs, washed allogeneic LR-RBCs will be associated with a comparable rise in hemoglobin concentration and will not be associated with evidence of increased hemolysis (CFH, haptoglobin) or acute kidney injury in the recipient.

Aim 1c - We hypothesize that RBC washing will reduce TRALI (neutral lipids, sCD40L, CCL5) and TACO (RBC-MPs, CFH) related BRMs in the RBC unit by greater than 80%.

AIM 2: *To demonstrate the extent to which point-of-care washing of allogeneic LR-RBCs impacts the recipient response to RBC transfusion when compared to standard-issue allogeneic LR-RBCs.*

Aim 2a - We hypothesize that RBC washing will reduce post-transfusion concentrations of validated lung injury-associated biomarkers (IL-6, IL-8, vWF, ICAM-1, RAGE, SP-D, PAI-1) in the transfusion recipient.

Aim 2b - We hypothesize that RBC washing will mitigate adverse physiologic consequences of RBC transfusion that have been associated with TACO (elevated mean arterial pressure, systemic vascular resistance, and pulmonary capillary wedge pressure).

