Specific Aim 1: The **primary feasibility outcome in aim 1a** will be the number and proportion of "off-protocol" allogeneic RBC transfusions administered during the study intervention period (day of surgery). A secondary feasibility outcome will be the time required for the RBC washing procedures (defined as the time from determination of RBC need by the clinical team to time of delivery of the RBC unit to the clinical team). This time will be computed for all patients and all transfusions during the study intervention period (in both the intervention and control cohorts). The **primary safety outcome in (aim 1b) include** the change in the RBC recipient's Hb concentration from pre- to post-transfusion as well as the concentration of CFH and haptoglobin following RBC transfusion. To assess the primary safety outcomes, samples for total Hb, CFH, and haptoglobin will be obtained prior to transfusion, as soon as possible after the first transfusion, but no later than 30 minutes following the first intervention/control RBC transfusion, as well as 6 hours (+/- 30 minutes) and 18 hours (+ / - 30 minutes) from the end of first study RBC transfusion for all study participants. We will also assess for clinical evidence of acute kidney injury throughout the hospitalization. Safety labs will also be drawn anytime on study day #5 if the patient is still in the hospital. The **primary efficacy outcome in aim 1c** will be the change in the concentration of neutral lipids [arachidonic acid, 5-hydroxyeicosatetraenoic acid (HETE), 12-HETE, 15-HETE], sCD40L, CCL5/RANTES, RBC-MPs, and CFH in the RBC component from the pre- to the post-wash phase. These data will allow us to calculate the CATS-related elimination rates for these BRMs, which have previously been associated with transfusion-related respiratory dysfunction and hemodynamic alterations. To balance assay costs while ensuring the scientific success of aim 1c, pre- and post-wash samples will be obtained/analyzed for the first 75 washed RBC units. If efficacy is not clearly established, we will continue to obtain both pre- and post-wash samples for 75 additional units.

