Statistical Considerations (prepared in collaboration with our statistical: Aim 1 is centered on the clinical and technical feasibility of on-demand RBC washing (hypothesis 1a). Feasibility is defined as the administration of protocol RBCs instead of "off-protocol" standard-issue RBCs. Simon's two-stage design will be used to determine if the protocol needs to be modified to prepare RBCs prior to the surgical procedure. The null hypothesis rate for feasibility is $p \leq 0.75$ versus the alternative that $p \geq 0.90$, where p is the probability of successfully preparing and administering the intervention RBCs. Stage 1 of the design will examine the first 16 cases randomized to RBC washing. If 12 or fewer transfusions were deemed "feasible", the protocol will be modified to pre-wash RBCs (see limitations). If 13 or more are feasible, an additional 32 cases will be evaluated. Should 39 or fewer (of the 48 studied) not be feasible, the protocol will be modified to pre-wash. If 40 or more cases meet the feasibility definition, the remainder of the study will go as originally planned. (Sample size/ design calculations details: PASS 2008, alpha=0.10, beta=0.10, Optimal design). The safety endpoint for aim 1 is the change in hemoglobin level (hypothesis 1b). The change in hemoglobin after the first transfused unit will be used as the primary safety measure. Wilcoxon rank sum tests will be used to compare change in hemoglobin levels between randomized groups. The change in concentrations of soluble BRMs (e.g.

neutral lipids; hypothesis 1c) will be assessed using paired t-tests. There is > 80% power to detect a 0.4 SD difference pre- to post-washing with 78 washed RBC products. Should there be fewer (due to feasibility), power will decrease. However, the magnitude of differences observed in preliminary data (92% reduction, Figure 4) is many times larger than an effect size of 0.4. Therefore, power for this hypothesis should not be a concern.

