The Aim 1c RBC washing efficacy outcome analyses evaluating the first 75 washed RBC units, comparing the pre-washed soluble biologic response modifier (BRM) concentrations to the post-washed unit concentrations, have been completed in collaboration with Drs. [name] and [name]. The Aim 1c findings indicate a decrease in the RBC micro-particle and cytokine concentrations, indicating the CATS washing procedure was effective in removing the BRM's that have previously been associated with transfusion-related cardiopulmonary dysfunction. However, the analyses also noted increased concentrations of cell free hemoglobin (CFH).

In an effort to further understand the potential relevance/clinical importance, if any, of the increase in CFH, we will obtain 20 evaluable hematocrit values between the two sites, both before and after the washing procedure. To accomplish this, a small sample of 2 mls. will be drawn from the RBC unit prior to performing the washing procedure and again at the conclusion of the washing procedure prior to administering the unit to the patient. This hematocrit analyses will be conducted locally at each site.

As we have completed the Aim 1c washing efficacy analyses defined a priori, we will no longer be collecting the 6 ml sample from the RBC bag prior to washing. Thus, the total amount of sample drawn from the RBC units will be less than it has been up to this point in the trial. Therefore, we would not anticipate any additional risks to the recipients of these washed allogeneic RBC units.

Our decision to test the hematocrit levels before and after washing in 20 RBC units is the result of our interactions with the lead statistician of this protocol who has estimated this to be a sufficient sample size to better understand the increase in cell free hemoglobin in relation to the total hemoglobin present in the allogeneic RBC units.

References

1. Fatalities Reported to FDA Following Blood Collection and Transfusion: Annual Summary for Fiscal Year 2011. US Food and Drug Administration, 2011.

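### The Aim 1 tests do not answer hypotheses 1b and 1c: BRM removal is tested against zero rather than 80%, and a comparable hemoglobin rise rests on a difference test alone

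*Combined protocol and SAP*

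**What the plan says.** **Hypothesis 1c.** The Specific Aims expect washing to lower TRALI and TACO "related BRMs in the RBC unit by greater than 80" percent. The listed BRMs are neutral lipids, sCD40L, CCL5, RBC microparticles and CFH; the text does not say whether every one must pass. In the Statistical Considerations the sentence on BRM concentrations ends "neutral lipids; hypothesis 1c) will be assessed using paired t-tests", with power above 80% claimed for a "0.4 SD difference pre- to post-washing with 78 washed RBC products". Outcome Measures, Specific Aim 1, adds an estimate: "These data will allow us to calculate the CATS-related elimination rates for these BRMs". It samples the first 75 washed units and sets a continuation rule: "If efficacy is not clearly established, we will continue to obtain both pre- and post-wash samples for 75 additional units". The Protocol Addendum reports that this analysis is finished: "The Aim 1c findings indicate a decrease in the RBC micro-particle and cytokine concentrations". On that basis it calls washing effective and stops pre-wash sampling. It also reports that CFH rose after washing.

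**Hypothesis 1b.** The Specific Aims expect a comparable hemoglobin rise and no sign of more hemolysis (CFH, haptoglobin) or acute kidney injury in recipients. Outcome Measures lists hemoglobin change, CFH and haptoglobin as primary safety outcomes and says kidney injury will be assessed. The Statistical Considerations narrow this: "The change in hemoglobin after the first transfused unit will be used as the primary safety measure". The test follows: "Wilcoxon rank sum tests will be used to compare change in hemoglobin levels between randomized groups". No margin or interval rule is given.

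Hypothesis 1a has its own two-stage decision rule and is not at issue.

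**The concern.** A test has to be capable of contradicting the claim it supports. Rejecting zero change says that washing removes something; it cannot separate a modest reduction from one above 80%. Failing to reject a hemoglobin difference may mean only that the trial was too small to see one. Both planned tests can therefore come out favourably while the stated hypothesis is false or unresolved.

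This matters in practice because the Addendum has already inferred efficacy from a decrease, with no stated comparison against 80%, while one of the BRMs named in 1c went up. The rise in CFH also makes recipient hemolysis the natural safety question. The plan draws the samples for it but does not state a comparison of the randomized arms for that purpose.

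**Working it through.** **Inputs.** 0.4 SD and 78 units (Statistical Considerations, Aim 1). 75 units sampled (Outcome Measures). Two-sided alpha 0.10 (Sample Size Considerations; its use for Aim 1 is an assumption, supported by the remark under Additional statistical considerations that a level above 0.05 was chosen). 154 transfused patients, equal allocation, hence 77 per arm. The documents give no hemoglobin SD, so 1b stays in SD units.

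**1. The plan's own figure.** Paired t-test, noncentrality 0.4 × √78 = 3.53. Power is 96.8% at two-sided 0.10 and 93.7% at 0.05. With 75 units it is 96.3% and 92.8%. The stated figure of more than 80% is correct, but it is power against no change.

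**2. What is enough for significance in 1c.** Smallest significant mean drop = t(0.95, 74)/√75 = 1.666/8.660 = 0.19 SD of the paired differences.

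**3. Why this says nothing about 80%.** Take an idealised case in which washing removes the same fraction f from every unit. The paired difference is f × pre-wash level, so t = √75 × mean(f × pre)/SD(f × pre) = √75/CV, where CV is the coefficient of variation of the pre-wash levels. The fraction f cancels: a small uniform cut and a 90% cut give the same t, significant whenever CV is below 8.660/1.666 = 5.2. Real data are noisier, but this shows that a t-test on concentrations is not a test of the proportion removed.

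**4. Clustering.** Several of the 75 units can come from one patient. Assuming 4 units per patient and an intraclass correlation of 0.1 to 0.3, the effective number is 75/(1 + 3 × 0.1) ≈ 57 down to 75/(1 + 3 × 0.3) ≈ 39. A test allowing for this would need 1.67/√57 = 0.22 SD to 1.69/√39 = 0.27 SD. The conclusion does not change.

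**5. Hemoglobin, 77 per arm, true shortfall 0.3 SD.**
- t-test: noncentrality 0.3 × √(77/2) = 1.86; missed 42% of the time at alpha 0.10.
- Wilcoxon, relative efficiency 0.955 for normal data: 0.3 × √(0.955 × 77/2) = 1.82; power = Φ(1.82 − 1.645) = 0.57; missed 43%. Simulation (200,000 runs, normal data) gives 43.5%, and 56% at alpha 0.05.
- By the same formula, a 0.2 SD shortfall is missed 67% of the time and a 0.4 SD shortfall 22%.

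**6. What an interval would give.** 90% CI half-width = 1.655 × √(2/77) = 0.27 SD. Shortfall that can be excluded with 80% power if the arms are truly equal = (1.645 + 0.842) × √(2/77) = 0.40 SD.

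**7. Coverage of the other safety outcomes.**
- Recipient CFH: an exploratory Aim 2c biomarker. If it enters the Aim 2 mixed models, their modified intention-to-treat rule moves washing-arm patients who received no washed cells into the control group.
- Haptoglobin: measured locally at the scheduled draws; no stated analysis.
- Kidney injury: no definition and no dedicated comparison. Organ failure scores (Aim 3, intention to treat) and adverse event monitoring cover it in part.

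**The case against.** The best defence is that this is an early-phase trial sized on Aim 2a, with a relaxed alpha and further trials foreseen. Elimination rates will be calculated and anyone can set them beside 80%. The pilot showed a median 92.2% microparticle reduction. The rank sum test by randomized group can still reveal harm. Much of this stands: an estimate for 1c will exist, and the point concerns how claims are supported, not lost data. But a relaxed alpha neither turns a test against zero into one against 80% nor turns non-significance into comparability. The pilot figure concerns one BRM in four units.

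Four stronger readings are tempting and are not supported:
- *That BRMs other than CFH fall short of 80%.* The Addendum reports decreases in microparticles and cytokines without giving their size, and a rise only for CFH.
- *That neutral lipids were not analysed.* The Addendum is a short justification for a hematocrit substudy, not a results report; its silence shows nothing.
- *That 0.4 SD or 0.19 SD equals some particular percentage reduction.* That needs an SD from the pilot quartiles and, on the log scale, a transform the plan does not mention. In simulation, an SD estimated from the quartiles of four values ranges from about 0.17 to 1.61 times the truth.
- *That the CFH rise was ignored, or that recipient CFH is wholly unanalysed.* The Addendum adds 20 pre/post-wash hematocrits, and Aim 2 samples recipient CFH. The first is a unit-level answer; the second is not a safety comparison by randomized arm.

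**Conclusion.** The mismatch is real and should be fixed. As written, 1c can be declared on a drop of 0.19 SD, and a hemoglobin shortfall of 0.3 SD passes unnoticed about 43% of the time. These figures assume alpha 0.10, 75 independent pairs and, for 1b, 77 per arm with roughly normal data. Whether 0.3 SD matters clinically cannot be judged from the documents. On the concentration outcome the protocol defines, CFH does not meet 1c; for the other BRMs the 80% question is open. The missing analyses for CFH, haptoglobin and kidney injury are the weaker part, closer to absent detail than to a wrong method, though the CFH finding gives them some weight. The plan's power arithmetic is not in error.

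**What to change.** 1. **BRMs.** From the existing 75 units, report the post/pre ratio with a confidence bound for every named BRM, including CFH and neutral lipids. Allow for units clustered within patients, and state a rule for values near the detection limit (two of the four pilot units had low pre-wash sCD40L). Claim removal above 80% only for markers whose upper one-sided 95% bound on the ratio is below 0.20; otherwise claim only a reduction where one is shown. State that CFH does not meet 1c. Label the rule post hoc, and do not use it to reopen the 75-unit extension.
2. **Hemoglobin.** Report the difference in hemoglobin rise by randomized arm with a 90% CI, and rest any wording about comparability on that interval. Call it estimation, since no margin has been justified.
3. **Other safety outcomes.** Add comparisons by randomized arm, with confidence intervals, of recipient CFH and haptoglobin (baseline-adjusted, at the scheduled draws), and of kidney injury under a definition fixed before the arms are compared.

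**Cost.** Analysis-plan wording and extra tabulation; no new patients, blood draws or unit samples. The 1c rule comes after the data were analysed, and some claims may become less favourable. Hemoglobin precision is limited to the half-width shown above. Kidney injury will be imprecise: the 90% CI half-width is 1.645 × √(2p(1 − p)/77), or 8, 11 and 12 percentage points for assumed rates of 10%, 20% and 30%, so only large differences would show.

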Study intervention: The intervention in this investigation will be implemented for all allogeneic RBCs administered on the day of surgery (intraoperative and postoperatively on Study Day 1). The decision to administer an allogeneic RBC transfusion will be left to the responsible clinical service and will not be prespecified in the study protocol. We have elected to leave this decision to the clinical service for the following reasons: 1) the target population frequently experiences major acute blood loss; in these circumstances, typical measures assessing the need for RBC transfusion (e.g. Hb) are often associated with unacceptable time delays and frequently do not reflect true red blood cell mass nor need for RBC transfusion; 2) this design facilitates a more meaningful understanding of the feasibility of RBC washing in clinical practice. Upon receiving an order for allogeneic RBC transfusion, the transfusion medicine service will prepare the RBC product according to the allocated treatment assignment (intervention versus control). Of note, all allogeneic RBC units at the two participating institutions undergo pre-storage leukocyte reduction.

Intervention cohort: For patients randomized to receive washed RBCs, all allogeneic RBCs **administered** on the day of surgery will be washed with the CATS device prior to transfusion. To account for the time

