The effects of storage duration will also be assessed. The mean age of the transfused blood products will be determined. This value will be used to test for effect modification (interaction with treatment). Specifically, the main effect of RBC age, its interaction action with treatment, time and the treatment-by-time interaction term will be used to determine if the biomarker trajectories are affected by RBC age. It is hypothesized that the washing protocol will attenuate the effects of age resulting in more uniform trajectories over the range of RBC age where as the unwashed RBC will show increases in biomarker values as RBC age increases.

Sample Size Considerations: The sample size for this clinical trial is based on the mechanistic outcomes detailed for Specific Aim 2a. Table 2 in Fremont et al. was used to provide estimates of the range of effect sizes for the biomarkers considered in this study.⁸⁰ Using an approximation of the standard deviation from the interquartile range ($SD \approx IRQ/1.35$), the median effect size was found to be 0.4. This magnitude of change would be relevant, and appropriate to power this study on. With equal allocation between the groups, the sample size for this study is estimated to be $n=78/group$ ($\alpha=0.10$, two-sided; see additional statistical considerations below). Actual power is expected to be higher on account of the repeated measures design. To allow for drop out and “non-feasible” cases, we plan to enroll and randomize patients until 154 patients have undergone surgery and had at least one transfusion on the operative day. We anticipate this may require randomizing up to 190 total patients. Any patients randomized and awaiting surgery when the 154th patient is achieved will also be included. The final sample size may be adjusted further based on the feasibility findings observed in the two-stage design.

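### The primary hemoglobin safety test uses pre-transfusion hemoglobin only by subtraction; it is valid under randomization but gives up power that baseline adjustment would recover

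*Combined protocol and SAP*

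**What the plan says.** Under Specific Aims, hypothesis 1b is that "washed allogeneic LR-RBCs will be associated with a comparable rise in hemoglobin concentration". Statistical Considerations makes this operational: "The change in hemoglobin after the first transfused unit will be used as the primary safety measure", and "Wilcoxon rank sum tests will be used to compare change in hemoglobin levels between randomized groups". No covariate, confidence interval, margin, standard deviation, detectable difference or power is given for this comparison.

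The baseline value exists. Under Outcome Measures, Specific Aim 1, "samples for total Hb, CFH, and haptoglobin will be obtained prior to transfusion", with a second draw no later than 30 minutes after the first study unit.

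Nothing elsewhere supplies an adjusted analysis. The section on predictor variables only lists what will be recorded. The mixed models are for the Aim 2 biomarkers. The sample size rests on Aim 2a, where "the median effect size was found to be 0.4". The only stated power figure belongs to the paired pre/post-wash comparison of Aim 1c: "There is > 80% power to detect a 0.4 SD difference pre- to post-washing with 78 washed RBC products".

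**The concern.** A change score fixes the coefficient of post on pre at 1. When the two values are imperfectly correlated and have similar spread, the true slope is below 1. Subtraction then over-corrects, and part of the pre-transfusion variation is left in the outcome as noise. Estimating the slope removes that noise from samples already drawn.

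The direction of the hypothesis makes this matter. Aim 1b looks for a comparable Hb rise, so a less sensitive test makes the hoped-for finding easier to reach. The trial is not sized on Hb, so there is no stated reserve of power. The question is also live: the Protocol Addendum reports higher cell-free hemoglobin in units after washing.

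The second consequence is conditional. If the arms happen to start at different Hb, the change score is shifted by (slope − 1) × imbalance. With a slope below 1, this credits the arm that starts lower with the larger rise.

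**Working it through.** **Plan's own figure.** Sample Size Considerations gives 78 per group at effect size 0.4, two-sided alpha 0.10. Power is not stated there; assuming 80%, n = 2(1.645 + 0.842)²/0.4² = 77.3, rounded up to 78. This reproduces, but it concerns the biomarkers. The 154 transfused patients give about 77 per arm, used below. Alpha 0.10 is carried over to Aim 1b.

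**Assumptions.** Pre-post correlation r from 0.3 to 0.9, equal pre and post standard deviations (SDs), and normal data unless stated. None of these is in the documents.

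**Power.** Var(change) = 2σ²(1 − r). The analysis of covariance (ANCOVA) residual variance is σ²(1 − r²). The ratio is (1 + r)/2. Take a true difference for which a t-test on change has 80% power at 77 per arm: its noncentrality is 1.645 + 0.842 = 2.486 before rounding of the parts.

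- Wilcoxon on change, efficiency 0.955: Φ(2.486·√0.955 − 1.645) = 78.4%.
- ANCOVA: Φ(2.486/√((1 + r)/2) − 1.645).

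| r | variance ratio | ANCOVA power | gap to Wilcoxon (points) | n per arm for ANCOVA to match the change t-test at 77 |
|---|---|---|---|---|
| 0.3 | 0.65 | 92.5% | 14.1 | 50 |
| 0.5 | 0.75 | 89.0% | 10.6 | 58 |
| 0.7 | 0.85 | 85.4% | 7.0 | 65 |
| 0.8 | 0.90 | 83.5% | 5.1 | 69 |
| 0.9 | 0.95 | 81.8% | 3.4 | 73 |

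Of each gap, about 1.6 points (80.0 − 78.4) is the price of ranks on normal data. A rank-based adjusted test would not recover all of it: with the factor √0.955 applied to the ANCOVA noncentrality, its power is about 91% at r = 0.3 and about 80% at r = 0.9.

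Simulation with a fixed deficit of 0.3 g/dL and SD 1.0 g/dL (both assumed) gives Wilcoxon power of 0.44, 0.56 and 0.78 at r = 0.3, 0.5 and 0.7. ANCOVA gives 0.60, 0.68 and 0.84. The gaps are 16, 12 and 6 points. At r = 0.9 both exceed 0.99, so for that deficit nothing is lost.

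**Unequal spread.** With SDpost/SDpre = 1.25 and r = 0.8 the slope is 1.25 × 0.8 = 1, and adjustment gains nothing over a t-test on change. With a ratio of 0.8, ANCOVA power is 93–97% in the same setting.

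**Type I error.** With no effect and random baselines, Wilcoxon on change rejects 9.7–10.1% of the time against a nominal 10%, with no average bias.

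**Given a realised imbalance, no effect.** The standard error of the baseline difference is √(2/77) = 0.161 SD.

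- Imbalance 0.16 SD (1 standard error): Wilcoxon on change rejects 9.4–9.9%, so there is no inflation.
- Imbalance 0.32 SD (about 2 standard errors, which chance alone produces in one direction or the other about 5% of the time): rejection is 26%, 22%, 17% and 13% at r = 0.3, 0.5, 0.7 and 0.9. Bias is about 0.23, 0.16, 0.10 and 0.03 SD in magnitude. ANCOVA stays at about 10%.

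**The case against.** Four points can be made for the plan.

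**Validity.** A reader might infer that the test ignores baseline Hb, or that it generally turns a baseline difference into a false effect. Neither is supported. Baseline is subtracted, and type I error is nominal under randomization. The raised rejection rates hold only given a sizeable imbalance, and they disappear when the slope is 1. This objection stands in full.

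**Systematic imbalance.** One might argue that an imbalance is likely because "The decision to administer an allogeneic RBC transfusion will be left to the responsible clinical service", and that this favours ANCOVA. The premise is plausible: randomization is at consent, the pre-transfusion sample comes later and only in transfused patients, and the clinical team is unblinded. The documents give no figure for it, and the inference fails. If one arm has a stable true Hb 0.3 g/dL lower, with no washing effect and independent noise at each draw (SD 1.0, assumed), Wilcoxon on change rejects about 10%. ANCOVA rejects 38%, 27% and 19% at r = 0.3, 0.5 and 0.7. Which method is biased depends on a model that cannot be checked from the documents. This stands as a caution about the fix.

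**Size of the gain.** The two draws bracket one unit, so r may be high, and a transfusion trigger that narrows pre-transfusion Hb would push the slope toward 1. Both are reasonable and would bring the gain to the low end. The documents do not settle it.

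**Outliers.** With major acute blood loss, ranks are defensible. With heavy-tailed t(3) errors (assumed), Wilcoxon on change beats linear ANCOVA, for example 90% against 85% power at slope 0.7 and deficit 0.3. This counts against a plain linear model but not against baseline adjustment. A rank test on baseline-adjusted residuals matched or beat Wilcoxon on change in the normal and t(3) settings examined, up to simulation error.

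**Conclusion.** The point holds as one of efficiency and of sensitivity to chance imbalance, not of validity. The planned test is correct in size but uses a measured baseline less well than it could. Against ANCOVA the cost is roughly 3 to 16 power points for r from 0.9 to 0.3, assuming equal SDs, normal data, 77 per arm and two-sided alpha 0.10. It can be near zero if the slope is close to 1 or the effect is large relative to the noise. Because no Hb standard deviation or correlation is given, the range cannot be narrowed. The loss deserves attention because it falls on a primary safety measure for which the desired answer is no difference.

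**What to change.** Make the primary Aim 1b analysis a baseline-adjusted comparison of Hb after the first unit, with randomized arm, pre-transfusion Hb and center (the stratification factor) in the model. Use a rank-based or robust regression, which keeps protection against outliers and yields a difference in g/dL. Replacing the values by their ranks would not give that estimate. Report the adjusted difference with its confidence interval (90% would match the trial's two-sided 0.10). Keep Wilcoxon on change as a sensitivity analysis. No further covariate, such as body weight, is required.

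Because pre-transfusion Hb is taken after randomization, report it by arm and set the two analyses side by side. If the arms differ noticeably in pre-transfusion Hb and the analyses disagree, neither should be read as decisive.

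The cost is a sentence or two in Statistical Considerations, with no new samples or patients. This does not by itself test whether the rise is comparable. That would need a prespecified margin against which to read the interval.
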